## 6.2 EXCLUSION CRITERIA

### Disease Related

1. Systemic chemotherapy with approved or investigational anticancer therapeutics, intended to treat underlying malignancy, within 3 weeks before the first dose of study treatment or 6 weeks for antibody therapy.
2. Dexamethasone at cumulative doses of greater than 160 mg or equivalent within 21 days prior to the first dose of study treatment is not allowed. Use of topical or inhaled steroids is acceptable.
3. Radiation therapy within 3 weeks before first dose of study drug.  
Radioimmunotherapy within 8 weeks before first dose of study drug.
4. Plasmapheresis is not permitted at any time during the Screening period or while the subject is receiving study treatment. If a subject has started Screening procedures requiring plasmapheresis, or is anticipated to require plasmapheresis during or after the Screening period, this patient will be considered ineligible and should not be enrolled.
5. Autologous SCT within the prior 8 weeks or allogeneic SCT within 16 weeks prior to initiation of study treatment. Patients with prior allogeneic SCT should not have evidence of moderate-to-severe graft-versus-host disease (as defined in [Filipovich 2005](#)) and must be approved by the **Sponsor's** study medical monitor.
6. Known hypersensitivity to any IMiDs, including rash

Approved

7. Prior pomalidomide exposure
  - a. For the dose-escalation portion of the study: Subjects requiring pomalidomide dose reduction or removal due to toxicity
  - b. For the dose-expansion portion of the study: Prior pomalidomide treatment of any duration
8. Known hypersensitivity/toxicity or intolerance to dexamethasone
9. Prior exposure to oprozomib
10. Hypersensitivity, intolerance, or inability to take antithrombotic prophylaxis

**Concurrent Conditions**

11. Major surgery within 3 weeks before first dose of study drug
12. Congestive heart failure (New York Heart Association Class III to IV), symptomatic ischemia, conduction abnormalities uncontrolled by conventional intervention, or myocardial infarction within 6 months before first dose of study drug
13. Acute active infection requiring systemic antibiotics, antivirals, or antifungals within 2 weeks before first dose of study drug
14. History of previous clinically significant GI bleed in the 6 months prior to first dose of study drug
15. Known or suspected human immunodeficiency virus (HIV) infection or patients who are HIV seropositive
16. Active hepatitis A, B, or C infection
17. Significant neuropathy (Grade 2 with pain or  $\geq$  Grade 3) at the time of the first dose of study drug
18. Other malignancy within the past 3 years except those considered cured by surgical resection; examples include some cases of:
  - a. Adequately treated basal or squamous cell carcinoma of the skin
  - b. Thyroid cancer
  - c. Carcinoma in situ of the cervix or breast
  - d. Prostate cancer with Gleason Score of 6 or less with stable prostate-specific antigen levels
19. Plasma cell leukemia
20. POEMS syndrome (polyneuropathy, organomegaly, endocrinopathy, monoclonal protein, and skin changes)
21. Known amyloidosis

Approved

22. Female patients who are pregnant or nursing
23. Uncontrolled diabetes or hypertension
24. Inability to swallow medication, inability or unwillingness to comply with the drug administration requirements, or GI condition that could interfere with the oral absorption or tolerance of treatment
25. Any contraindication to oral hydration (eg, preexisting cardiac impairment or fluid restriction)
26. Any clinically significant psychiatric, social, or medical condition that, in the opinion of the investigator, could increase patient risk, interfere with protocol adherence, or affect a patient's ability to give informed consent

## 7 SUBJECT SCREENING

A signed and dated informed consent form will be obtained before any screening procedures are performed. Evaluations obtained as part of routine medical care and performed during the screening period may be used in place of the study-specific evaluations, provided they meet the time windows described below. Subjects will acknowledge and agree to the possible use of this information for the study by giving informed consent. The screening period for a particular subject commences at the point, after informed consent is signed, at which the subject undergoes the first study-specific screening assessment, and must be completed within 28 days of receiving the first dose of study drug.

## 8 SUBJECT ENROLLMENT

All subjects who sign consent will be assigned a unique study number. This number will be used to identify the subject throughout the clinical study and must be used on all study documentation related to that subject. The **Sponsor's** study medical monitor or designee will review the subject's information before enrollment. Only subjects who are approved by the **Sponsor's** study medical monitor will be allowed to enroll into the study. A minimum time of 24 hours during weekdays (Monday through Friday) will be required for the **Sponsor's** study medical monitor or designee to approve a subject for enrollment, and additional time may be required when approval is sought during a weekend or holiday. Subjects are only considered enrolled when the **Sponsor's** study medical monitor or designee approves the patient for enrollment.

Approved

## 9 STUDY DRUG

**No changes in drug product, dosage, or treatment-regimen occurred in this protocol amendment from the previous version.**

### 9.1 OPROZOMIB

#### 9.1.1 OPROZOMIB PHYSICAL DESCRIPTION

Oprozomib is a synthetic small molecule peptide bearing the chemical name N-((S)-3-methoxy-1-((S)-3-methoxy-1-((S)-1-((R)-2-methyloxiran-2-yl)-1-oxo-3-phenylpropan-2-ylamino)-1-oxopropan-2-ylamino)-1-oxopropan-2-yl)-2-methylthiazole-5-carboxamide. The molecular formula is C25H32N4O7S and the molecular weight is 532.61. It specifically functions as an inhibitor of the CT-L activity of the 20S proteasome, which leads to the accumulation of protein substrates within the cell and induction of apoptosis.

#### 9.1.2 OPROZOMIB FORMULATION

Oprozomib will be provided as a tablet for oral administration. Oprozomib ER Tablets are intended to release greater than or equal to 75% (Quantity) of the total dose of oprozomib over approximately 8 hours.

Oprozomib ER Tablets are white to off-white tablets manufactured at 5 dosage strengths:

- Oprozomib 150 mg oval shape tablets are debossed with “H” on one side and contain 150 mg of oprozomib
- Oprozomib 180 mg oval shape tablets are debossed with “I” on one side and contain 180 mg of oprozomib
- Oprozomib 210 mg oval shape tablets are debossed with “J” on one side and contain 210 mg of oprozomib
- Oprozomib 240 mg oval shape tablets are debossed with “K” on one side and contain 240 mg of oprozomib
- Oprozomib 270 mg oval shape tablets are debossed with “L” on one side and contain 270 mg of oprozomib

The excipients for the drug product are lactose monohydrate, microcrystalline cellulose, sodium lauryl sulfate, magnesium stearate, hydroxy propyl methyl cellulose, and Opadry II White. The drug substance-to-excipient ratio is the same in all 5 dosage strengths.

Approved

### **9.1.3 OPROZOMIB PACKAGING AND LABELING**

The Oprozomib ER Tablets will be available in 150, 180, 210, 240, and 270 mg of oprozomib. Details are provided in the Pharmacy Manual.

### **9.1.4 OPROZOMIB STORAGE**

Oprozomib must be stored at room temperature (15°C–30°C; 59°F–86°F) in a secured area to which access is limited to appropriate study personnel.

## **9.2 POMALIDOMIDE**

Pomalidomide is available as a capsule containing 1, 2, 3, and 4 mg of pomalidomide drug substance for oral administration. Additional product information is provided in the Pomalidomide Prescribing Information (Celgene Corporation, 2013).

### **9.2.1 POMALIDOMIDE PHYSICAL DESCRIPTION**

POMALYST is available in 1-mg, 2-mg, 3-mg, and 4-mg capsules for oral administration. Each capsule contains pomalidomide as the active ingredient and the following inactive ingredients: mannitol, pregelatinized starch, and sodium stearyl fumarate. The 1-mg capsule shell contains gelatin, titanium dioxide, FD&C blue 2, yellow iron oxide, white ink, and black ink. The 2-mg capsule shell contains gelatin, titanium dioxide, FD&C blue 2, yellow iron oxide, FD&C red 3, and white ink. The 3-mg capsule shell contains gelatin, titanium dioxide, FD&C blue 2, yellow iron oxide, and white ink. The 4-mg capsule shell contains gelatin, titanium dioxide, FD&C blue 1, FD&C blue 2, and white ink.

### **9.2.2 POMALIDOMIDE PACKAGING AND LABELING**

Pomalidomide is commercially available as capsules for oral administration.

### **9.2.3 POMALIDOMIDE STORAGE**

Store at 20°C–25°C (68°F–77°F); excursions permitted to 15°C–30°C (59°F–86°F). See USP Controlled Room Temperature.

Approved

### 9.3 DEXAMETHASONE

Dexamethasone, a synthetic adrenocortical steroid, is available as tablets containing 4 or 6 mg of dexamethasone drug substance for oral administration.

#### 9.3.1 DEXAMETHASONE PACKAGING AND LABELING

Dexamethasone is commercially available both as tablets for oral administration and as various sterile formulations for parenteral administration. Additional information is provided in the Dexamethasone Prescribing Information ([Pfizer Laboratories, 2012](#)).

#### 9.3.2 DEXAMETHASONE STORAGE

Dexamethasone is not to be stored above 30°C (86°F). Additional storage and usage instructions are provided in the Dexamethasone Prescribing Information ([Pfizer Laboratories, 2012](#)).

### 9.4 STUDY DRUG ACCOUNTABILITY

**The Sponsor** (or designee) and the investigator will maintain records of each shipment of investigational product (IP). Upon receipt of IP, the designated recipient at the study site will inspect the shipment, verify the number and condition of the bottles or blister packs, and prepare an inventory or drug accountability record. The records will document shipment dates, method of shipment, batch numbers, product presentation, quantity of bottles or blister packs contained in the shipment, and dispensation to individual subjects using the subject identification number.

Sites will be required to record and document subject compliance with oprozomib, pomalidomide, and dexamethasone dosing.

Additional details for oprozomib are provided in the Pharmacy Manual.

Approved

## 10 OPROZOMIB TREATMENT ADMINISTRATION

It is recommended that oprozomib not be taken on an empty stomach. Subjects will be instructed to take the oprozomib doses after eating with approximately 8 ounces of water. On the PK collection days, dosing of oprozomib in relation to the meal intake (within 2 hours before and 1 hour after dose) will be recorded.

### 10.1 OPROZOMIB TREATMENT ADMINISTRATION

Oprozomib ER Tablets will be administered in single daily doses. Oprozomib will be administered orally, once daily for 5 consecutive days every other week ([5/14 schedule] ie, on Days 1–5 and 15–19) or once daily for 2 consecutive days of every week ([2/7 schedule] ie, on Days 1, 2, 8, 9, 15, 16, 22, and 23) of each 28-day treatment cycle. Treatment with oprozomib will continue until disease progression, unacceptable toxicity, or study treatment discontinuation for any reason. On days on which oprozomib and dexamethasone are administered concurrently, dexamethasone should be taken at least 30 minutes before oprozomib. Subjects are to be informed not to break, chew, or crush the Oprozomib ER Tablets.

In the dose-escalation and dose-expansion portions of the study, subjects who permanently discontinue pomalidomide or oprozomib may continue on study. If both pomalidomide and oprozomib are permanently discontinued, study treatment will be discontinued but the subject will be followed until disease progression.

### 10.2 POMALIDOMIDE TREATMENT ADMINISTRATION

Pomalidomide will be administered at 4 mg, orally, in the fasted condition (2 hours before or after meals) according to the Prescribing Information ([Celgene Corporation, 2013](#)) on Days 1–21. Pomalidomide may be taken with water. Subjects are to be informed not to break, chew, or open the capsules.

The starting dose of pomalidomide for this study is 4 mg once daily, orally, on Days 1–21 of repeated 28-day cycles until disease progression. Pomalidomide may be given at the same time as dexamethasone; however, dexamethasone must be given at least 30 minutes prior to oprozomib.

Approved

### 10.3 DEXAMETHASONE TREATMENT ADMINISTRATION

Dexamethasone will be administered at 20 mg, orally, on Days 1, 2, 8, 9, 15, 16, 22, and 23 of each 28-day cycle. On days of concurrent oprozomib and dexamethasone administration, dexamethasone should be taken at least 30 minutes prior to oprozomib. Subjects may take dexamethasone with or without food. Dexamethasone may be given at the same time as pomalidomide; however, dexamethasone must be given at least 30 minutes prior to oprozomib.

Dexamethasone may be administered intravenously (IV), if needed, at the investigator's discretion, but IV dexamethasone will not be provided by the sponsor.

### 10.4 DOSE MODIFICATION GUIDELINES

This section provides dose reduction and other modification guidelines for oprozomib, pomalidomide, and dexamethasone to manage possible toxicity. Administration of oprozomib or pomalidomide will be discontinued in the event of a treatment-related toxicity that, in the opinion of the investigator, warrants permanent discontinuation.

Monotherapy with dexamethasone is not allowed in the dose-escalation and dose-expansion portions of the study.

Exceptions to the dose modification guidelines are permitted with written approval from the Sponsor's study medical monitor.

#### 10.4.1 DOSE REDUCTIONS

For this study, the initial cohort will start at an oprozomib dose level of 150 mg for the 5/14 schedule and 210 mg for the 2/7 schedule. For these subjects, oprozomib or pomalidomide or dexamethasone dose reductions are discouraged during the DLT assessments. Subjects requiring dose reductions in Cycle 1 will be referred to the CSRC for determination if the subject is considered evaluable and for DLT assessment per [Section 5.1.4](#). Dose reduction levels for oprozomib subsequent to Cycle 1 for the 5/14 and 2/7 dosing schedules are provided in [Table 9](#) and [Table 10](#), respectively. Modifications of the dose of oprozomib will occur in up to three 30-mg decrements down to a minimum dose of 150 mg. Additional reductions will be managed by schedule change.

Approved

**Table 9 Dose Decrements for Oprozomib – 5/14 Schedule**

Nominal Dose Level	Reduced Oprozomib Doses		
	First Dose Reduction	Second Dose Reduction	Third Dose Reduction
150 mg	Continue 150 mg AND change to 3/14 a schedule (Days 1, 2, 3, 15, 16, 17 of 28-day schedule)	D/C oprozomib	NA
180 mg	Dose – 30 mg	Dose – 30 mg AND change to 3/14 schedule (Days 1, 2, 3, 15, 16, 17 of 28-day schedule)	D/C oprozomib
210 mg	Dose – 30 mg	Dose – 60 mg	Dose – 60 mg AND change to 3/14 schedule (Days 1, 2, 3, 15, 16, 17 of 28-day schedule)
≥ 240 mg	Dose – 30 mg	Dose – 60 mg	Dose – 90 mg

5/14 = Dosing on Days 1–5 and 15–19; D/C = discontinue; NA = not applicable.

a The minimum oprozomib dose is 150 mg; thus, additional reductions will be managed by schedule change to the 3/14 schedule where doses of oprozomib will be skipped on Days 4, 5, 18, and 19.

**Table 10 Dose Decrements for Oprozomib – 2/7 Schedule**

Nominal Dose Level	Reduced Oprozomib Doses		
	First Dose Reduction	Second Dose Reduction	Third Dose Reduction
210 mg	Dose – 30 mg	Dose – 60 mg	Dose – 60 mg AND change to 1/7 a schedule (Days 1, 8, 15, 22 of 28-day schedule)
≥ 240 mg	Dose – 30 mg	Dose – 30 mg	Dose – 90 mg

2/7 = Dosing on Days 1, 2, 8, 9, 15, 16, 22, and 23.

a The minimum oprozomib dose is 150 mg; thus, additional reductions will be managed by schedule change to the 1/7 schedule where doses of oprozomib will be skipped on Days 2, 9, 16, and 23.

The dose reduction levels for pomalidomide are provided in [Table 11](#). Dose adjustments should, in general, follow the instructions provided in the Pomalidomide Prescribing Information 2013 ([Celgene Corporation, 2013](#)).

Approved

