**Table 6 Primary Dose-Escalation Path for Oprozomib on the 2/7 Schedule with Pomalidomide 4 mg in Phase 1b**

Cohort 2/7 Schedule	Oprozomib Dose (mg/day)	Pomalidomide Dose (mg/day)
101a (initial cohort)	210	4
201a	240	4
301a	270	4

2/7 = Dosing on Days 1, 2, 8, 9, 15, 16, 22, and 23; MTD = maximum tolerated dose.

Note: This is an example of the primary dose-escalation cohort. Dose escalation will continue in 30-mg increments of oprozomib until the MTD is identified.

If Cohort 101a exceeds the MTD, or at the sponsor's discretion, the alternative path 1 described in [Table 7](#) may be followed.

**Table 7 Alternative Dose-Escalation Path 1 for Oprozomib on 2/7 Schedule with Pomalidomide in Phase 1b if Cohort 101a Exceeds the MTD or at Sponsor Discretion**

Cohort 2/7 Schedule	Oprozomib Dose (mg/day)	Pomalidomide Dose (mg/day)
101b	210	3
201b	240	3
301b	270	3

2/7 = Dosing on Days 1, 2, 8, 9, 15, 16, 22, and 23; MTD = maximum tolerated dose.

If Cohort 101b exceeds the MTD, or at the sponsor's discretion, the alternative path 2 described in [Table 8](#) may be followed.

**Table 8 Alternative Dose-Escalation Path 2 for Oprozomib on 2/7 Schedule with Pomalidomide in Phase 1b if Cohort 101b Exceeds the MTD or at Sponsor Discretion**

Cohort 2/7 Schedule	Oprozomib Dose (mg/day)	Pomalidomide Dose (mg/day)
101c	210	2
201c	240	2
301c	270	2

2/7 = Dosing on Days 1, 2, 8, 9, 15, 16, 22, and 23; MTD = maximum tolerated dose.

Approved

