**Table 13 Guidelines for Dose Modification of Oprozomib/Placebo and Pomalidomide for Hematologic Toxicities**

Findings	Oprozomib	Pomalidomide
Findings on Day 1 of Cycle		
Recommended Action		
Platelets $< 25 \times 10^9/L$	Hold dose a until recovery $\geq 25 \times 10^9/L$ ; restart at previous dose.	Not applicable.
Platelets $< 30 \times 10^9/L$	Not Applicable.	Hold dose a , follow CBCs. Hold prophylactic anticoagulation until platelets return to $\geq 30 \times 10^9/L^a$ , then resume at 1 dose decrement.
ANC $< 0.5 \times 10^9/L$ or febrile neutropenia (fever $\geq 38.5^\circ C$ and ANC $< 1.0 \times 10^9/L$ )	Hold dose a . Add colony stimulating factor b With resolution to $\geq 1.0 \times 10^9/L$ , restart at previous dose.	Hold dose a . Add colony stimulating factor b With resolution to $\geq 0.5 \times 10^9/L$ , restart at 1 dose decrement.
Findings on Subsequent Days of Cycle		
Recommended Action		
Platelets 25 to $< 50 \times 10^9/L$ without $\geq$ Grade 2 bleeding/hemorrhage	Full dose.	Full dose.
Platelets 25 to $< 50 \times 10^9/L$ with $\geq$ Grade 2 bleeding/hemorrhage	Hold dose a until platelets return to $\geq 50 \times 10^9/L$ and/or bleeding is controlled, then resume at 1 dose decrement.	Hold dose a until platelets return to $\geq 50 \times 10^9/L$ and/or bleeding is controlled, then resume at 1 dose decrement.
Platelets $< 25 \times 10^9/L$ or thrombocytopenia with $\geq$ Grade 2 bleeding/hemorrhage	Hold dose a until recovery to $\geq 25 \times 10^9/L$ ; restart at 1 dose decrement.	Hold dose a . Hold prophylactic anticoagulation until platelets return to $\geq 30 \times 10^9/L^a$ , then resume at 1 dose decrement.
Neutropenic fever (ANC $< 1.0 \times 10^9/L$ and single temperature $> 38.3^\circ C$ or temperature $> 38.0^\circ C$ sustained for more than 1 hour)	Hold dose a ; follow CBC at least 3 times per week. Add colony stimulating factor b With resolution of fever and ANC $\geq 1.0 \times 10^9/L$ , restart at 1 dose decrement.	Hold dose a ; follow CBCs. Add colony stimulating factor b . With resolution of fever and ANC $\geq 1.0 \times 10^9/L$ , restart at 1 dose decrement.

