ANC $< 0.5 \times 10^9/L$	Hold dose a ; follow CBC at least 3 times per week; administration of colony stimulating factor b is permitted. Resume at full dose if ANC $\geq 0.5 \times 10^9/L$ within $< 7$ days. Resume at 1 dose decrement if ANC returns to $\geq 0.5 \times 10^9/L \geq 7$ days.	Hold dose a until ANC increases to $\geq 0.5 \times 10^9/L$ . Administer colony stimulating growth factor b . Resume at 1 dose decrement each subsequent decrease to $< 0.5 \times 10^9/L$ .

ANC = absolute neutrophil count; CBC = complete blood count.

a The maximum allowed dose interruption is 4 weeks for treatment-related toxicity.

b Colony stimulating factors such as filgrastim or sargramostim as examples.

Approved

Additional guidance regarding hematologic toxicities and dosing actions is as follows:

- To initiate a new cycle of pomalidomide, the neutrophil count must be at least 500 per  $\mu\text{L}$  and the platelet count must be at least 50,000 per  $\mu\text{L}$ . If toxicities continue to occur after dose reductions down to 1 mg, then discontinue pomalidomide.
- Nontreatment-related events: If the toxicity resolves to  $\leq$  Grade 1 or baseline and the toxicity is not treatment-related, oprozomib may be restarted at the same dose level
- If required by continued or recurrent toxicity, a second or third dose reduction of oprozomib may be permitted after discussion with the **Sponsor's** study medical monitor. No more than 3 dose reductions down to a minimum of 150 mg will be permitted for an individual subject on study and additional reductions will be managed by schedule change. If toxicity continues, oprozomib should be discontinued.

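### Table 10 (2/7 schedule, 240 mg or more): the second oprozomib reduction repeats the first, so the dose does not fall when toxicity recurs

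*Protocol*

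**What the plan says.** Protocol Section 10.4.1 gives the rule in words: "Modifications of the dose of oprozomib will occur in up to three 30-mg decrements down to a minimum dose of 150 mg". Two tables then spell it out by schedule.

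- Table 9 (5/14), nominal 240 mg or more: "Dose – 30 mg Dose – 60 mg Dose – 90 mg".
- Table 10 (2/7), nominal 210 mg: 30 mg below nominal, then 60 mg below, then 60 mg below with a move to once-weekly (1/7) dosing.
- Table 10 (2/7), nominal 240 mg or more: "Dose – 30 mg Dose – 30 mg Dose – 90 mg".
- Table 10, footnote a: "The minimum oprozomib dose is 150 mg; thus, additional reductions will be managed by schedule change to the 1/7 schedule".

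Table 13 tells sites when to use these entries. For example, after platelets fall below 25 × 10^9/L later in a cycle, oprozomib is held until recovery, with the instruction to "restart at 1 dose decrement". The guidance under Table 13 says that, for toxicity that persists or comes back, "a second or third dose reduction of oprozomib may be permitted after discussion with the" sponsor's medical monitor, and sets a cap: "No more than 3 dose reductions down to a minimum of 150 mg will be permitted for an individual subject on study".

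On pomalidomide, the Day 1 row of Table 13 holds the drug at platelets below 30 × 10^9/L and resumes it one decrement lower once the count is back to 30 or more. The guidance under the table requires at least 50,000 per µL before a new pomalidomide cycle begins.

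**The concern.** In the 240 mg or more row of Table 10 the second entry is the same as the first. If entries are measured from the nominal dose, the second reduction changes nothing. It applies to exactly the subjects who have already been reduced once and have had toxicity again.

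Followed as printed, such a subject restarts on the dose at which the second event occurred, and one of the three permitted reductions has been spent without lowering exposure. The consequence is not confined to platelets. Table 13 also calls for a decrement after neutropenic fever, and Table 14 does so for neuropathy, gastrointestinal toxicity, fatigue, and renal and liver events. Low platelets are still the obvious example: Section 3.4.2 reports Grade 4 thrombocytopenia as a DLT on the 2/7 schedule in both Study 2011-001 and Study 2012-001. Those were DLTs, not recurrences on a reduced dose, so they show that the toxicity is relevant, not how often this row would be used.

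**Working it through.** **Inputs.** The decrements in Tables 9 and 10, the 150 mg minimum and the 30-mg step rule in Section 10.4.1, and the 2/7 example cohorts in Tables 6 to 8. Let N be the nominal dose and d₁, d₂, d₃ the printed decrements.

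**Two possible readings.**

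- From nominal: dose after reduction k = N − dₖ.
- Stepwise: dose after reduction k = previous dose − dₖ.

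| Row | Decrements (mg) | From nominal (mg) | Stepwise (mg) |
|---|---|---|---|
| Table 9, 180 | 30, 30 (+ 3/14) | 150, 150 | 150, 120 |
| Table 9, 210 | 30, 60, 60 (+ 3/14) | 180, 150, 150 | 180, 120, 60 |
| Table 9, ≥ 240, at 240 | 30, 60, 90 | 210, 180, 150 | 210, 150, 60 |
| Table 10, 210 | 30, 60, 60 (+ 1/7) | 180, 150, 150 | 180, 120, 60 |
| **Table 10, ≥ 240, at 240** | **30, 30, 90** | **210, 210, 150** | **210, 180, 90** |
| **Table 10, ≥ 240, at 270** | **30, 30, 90** | **240, 240, 180** | **240, 210, 120** |
| **Table 10, ≥ 240, at 300** | **30, 30, 90** | **270, 270, 210** | **270, 240, 150** |

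**Which reading is meant.** Stepwise, the four rows above the bold ones all fall below 150 mg. From nominal, all four stay at or above it. The tables are therefore counted from nominal.

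**The row in question, from nominal.** At 240 mg the steps are 240 − 210 = 30, 210 − 210 = 0 and 210 − 150 = 60 mg. At 270 mg they are 270 − 240 = 30, 240 − 240 = 0 and 240 − 180 = 60 mg. The rule of 30-mg steps is broken twice.

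**The same row, stepwise.** It ends at 90 mg from 240 and at 120 mg from 270, both under the minimum. From 300 it ends at exactly 150 mg, so the minimum is respected there, but the third step is still 90 mg. Neither reading agrees with Section 10.4.1.

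**With 60 mg as the second decrement, from nominal.** 240 gives 210, 180, 150; 270 gives 240, 210, 180; 300 gives 270, 240, 210. Every step is 30 mg, nothing falls below 150 mg, and the row matches Table 9.

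**Size.** After a second reduction the printed dose is 30 mg above the intended one: 210 against 180 mg (30/180 = 17% higher) or 240 against 210 mg (30/210 = 14% higher). Of the nine example 2/7 cohorts, six are at 240 mg or more (201a–c and 301a–c). On the primary path alone it is two of three (201a and 301a).

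**Could the repeat be deliberate?** The only other repeated 30 mg entry is the 180 mg row of Table 9. There the second entry comes with a change to 3/14 dosing, so exposure still falls. The Table 10 row has no such change.

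**Platelets and pomalidomide.** The Day 1 row allows resumption from 30 × 10^9/L and the text requires 50 × 10^9/L. The two disagree for counts from 30 to below 50 × 10^9/L when a cycle is started or resumed.

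**The case against.** The case for leaving this alone, or treating it as a minor typo, has several parts.

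- **It rests on one digit in one cell.** A 6 misprinted or misread as a 3 would produce it, and Table 10 is not repeated elsewhere in the documents. This cannot be excluded, and the cell should be checked against the signed protocol. Nothing specific points to a misreading: the row is complete and the rest of the table is coherent.
- **A sensible clinician would take off another 30 mg.** That gives 180 from 240 or 210 from 270, which are the intended doses, and Section 10.4.1 supports doing so. This stands as a reason why harm may not follow. It works only if the site sets the table aside, and Section 10.4 requires the medical monitor's written approval for departures from the guidelines.
- **The medical monitor is consulted at this step.** True, and it is the main safeguard. It makes the error catchable but does not correct the table that the monitor would also be using.
- **The lost step is only intermediate.** Also true. The third dose is the same either way (150 from 240, 180 from 270), and schedule change remains available afterwards.
- **The b and c cohorts may never open.** They require the starting cohort to exceed the MTD, or sponsor discretion. Cohorts 201a and 301a are still affected.
- **The platelet rules can be followed together by applying the stricter one.** They can, and that is the right resolution. But the Table 13 row does say to resume pomalidomide at the lower count, so it needs to say which rule governs.

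**Conclusion.** The concern holds. As written, Table 10 gives no dose reduction at the second step for nominal doses of 240 mg or more on 2/7, followed by a 60 mg drop at the third. This contradicts Section 10.4.1 and differs from the matching row of Table 9. The excess at the second step is 30 mg per dose.

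The conclusion rests on two assumptions: that the cell reads as printed, and that decrements are counted from nominal, which the other rows and the 150 mg minimum require. It is almost certainly a slip for 60 mg.

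It is an operative dosing instruction for subjects with recurrent toxicity and should be corrected, but its reach is limited. The 210 mg row is sound. Tables 9 and 10 apply after Cycle 1, so DLT and MTD assessment are unaffected, as are sample size and analysis. Amendment 3, in which this table appears, was not implemented before the program ended; because Section 9 states that dosing was unchanged from the previous version, the active Amendment 2 probably carried the same cell, but that is inference. The platelet mismatch is real and smaller.

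**What to change.** In Table 10, row 240 mg or more, change the second reduction to 60 mg below the nominal dose. A line under Tables 9 and 10 stating that all decrements are counted from the nominal dose would remove the remaining ambiguity.

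In the Day 1 pomalidomide row of Table 13, state that a new cycle is neither started nor resumed until platelets are at least 50 × 10^9/L, the stricter rule that the text already makes mandatory.

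The cost is one table cell and one or two clarifying phrases, by amendment or administrative letter. Sample size, DLT rules and analyses do not change. Any later protocol that reuses Table 10 should carry the corrected row.
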